8.2.7. Analysis of Safety Endpoint

All safety results will be presented based on the Safety Analysis Set. All TEAEs will be summarized by treatment arm. Subject incidence of TEAEs will be summarized by treatment arm and by MedDRA (Version 23 or higher) system organ class and preferred term. For each coded medical term, the proportion of subjects who experience at least one treatment-emergent:

- adverse event(s);
- adverse event(s) related to treatment
- serious adverse event(s);
- serious adverse event(s) related to treatment
- adverse event(s) by severity (mild, moderate, severe);
- adverse event(s) leading to treatment/study discontinuation, or
- serious adverse event(s) leading to treatment/study discontinuation will be reported.

A listing of death(s), subjects who died of any cause during the study, will be presented.

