7.4. AE Collection/Reporting Period

The AE collection/reporting period will begin after the subject has been randomized. Investigators should assess for AEs at each visit. In addition, study subjects should be instructed to report any AE that they experience to the investigator.

All AEs, regardless of perceived relationship to study product, will be reported and documented in a timely manner. In addition, the worsening of a medical condition previously reported in the medical history should also be recorded as an AE.

The AE description will include the nature of the experience (AE term), the start date, the end date, the severity of each sign or symptom, the seriousness of the event or experience, relationship to study treatment, the course of action taken, and the outcome of the experience. It will be indicated if the AE caused the subject to be discontinued from the study.

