8.2. Planned Analysis and Data Summaries

8.2.1. General Analysis Techniques

In general, summaries of endpoints will consist of descriptive statistics. Data will be summarized by treatment group, overall and/or by visit, if applicable. Due to each subject serving as their own control and receiving both treatments (one treatment per knee), the same subjects will be counted once within each treatment group according to the treatment received and/or randomized in for each knee. Subjects who only have one knee treated will only be counted in the treatment group that the knee received. Data processing, tabulation of descriptive statistics, and any graphical representations will be performed primarily using SAS (release 9.4 or higher). If the use of other software is warranted, details will be included in the clinical study report (CSR).

Summaries of continuous variables will display the number of subjects and/or knees with available data (n), the mean, median, standard deviation, minimum, and maximum values at each time point. For categorical variables, the number and percentage of subjects and/or knees that are in each category will be provided. The denominator for percentages will be all relevant subjects and/or knees in a particular analysis, including those for whom data are not reported or missing.

Formal statistical testing will be conducted utilizing two-sided tests at a significance level of 0.05. Corresponding 95% confidence intervals (CIs) will be presented for appropriate endpoints.

Additional analyses to characterize the safety and/or efficacy may be conducted. These additional analyses will be included in the Statistical Analysis Plan. Any ad hoc summaries/analyses conducted after database lock will be included in the CSR and labeled as *ad hoc*.

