8.3.2. Randomization

All subjects who meet all inclusion criteria and no exclusion criteria will be randomized in a 1:1 ratio to receive the PREVENA RESTOR ARTHRO•FORM™ Incision Management System or the control in either right or left knee. Each subject will receive both treatments (one treatment per knee). A randomization schedule, including randomization numbers and treatment assignments, will be generated and maintained centrally in the web-based clinical database management system. Once randomized, a subject's assignment cannot be altered or changed; a subject should not be randomized twice. The randomization schedule will be kept blind to any person who is involved in the daily operations of the study. It will only be accessible to the study biostatisticians who generate and review the schedule, and the vendor's team members (if an EDC vendor is utilized) who are involved in reviewing the schedule and uploading the schedule.

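### Section 8.2.7 tabulates all TEAEs by treatment arm although every subject is in both arms, and the plan gives no rule for assigning an event to an arm

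*Combined protocol and SAP*

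**What the plan says.** All references are to the combined protocol and SAP.

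- **Tabulation (8.2.7).** "All TEAEs will be summarized by treatment arm". The unit is the subject: "Subject incidence of TEAEs will be summarized by treatment arm and by MedDRA (Version 23 or higher) system organ class and preferred term". Proportions are then listed for AEs, SAEs, related events, severity grades and events leading to discontinuation.
- **Design (8.3.2).** Every randomized subject gets both treatments, one on each knee.
- **Counting rule (8.2.1).** "the same subjects will be counted once within each treatment group according to the treatment received and/or randomized in for each knee".
- **What is collected (7.4).** "All AEs, regardless of perceived relationship to study product, will be reported and documented in a timely manner", so systemic events are in scope.
- **AE record (7.4).** "The AE description will include the nature of the experience (AE term), the start date, the end date", then severity, seriousness, relationship, action taken, outcome, and whether the event led to discontinuation. No knee or side is named.
- **Relatedness (7.2.1).** One judgement, related or not related to the study product. The synopsis and section 1.4 list both the ciNPT system and the silver-containing dressing as study products.
- **Where the knee is recorded.** SSCs are assessed for each knee (4.15.1, 5.2.5 to 5.2.8). Knee-related admissions and ED visits record the responsible knee (4.15.4). The Safety Analysis Set is analysed by the treatment each knee received (8.1).

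**The concern.** In a parallel-group trial, a subject's arm fixes the arm of every event. Here it does not. A blister under one dressing belongs to a knee and so to an arm; a pulmonary embolism belongs to neither. Section 1.3 itself names pulmonary embolism and cardiac arrhythmia as risks of the simultaneous bilateral procedure, so such events are foreseeable.

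The instruction to summarize all TEAEs by arm leaves three ways to handle a systemic event: enter it in both arms, put it in one arm arbitrarily, or omit it. The first makes the arms look alike, the second creates a difference with no meaning, and the third contradicts the instruction. For local events the arm can be known only if the knee is captured, and 7.4 does not list it.

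At stake is the descriptive safety comparison. A by-arm table with nearly equal totals could be read as reassurance about the device when the equality was built in by the counting.

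**Working it through.** The safety sections state no rate or computed figure, so there is no figure of the plan's own to reproduce. The check has two parts.

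**1. Following one event through the stated rules.** Suppose one of 52 subjects (section 3.1) has a pulmonary embolism after randomization.

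- 7.4 requires it to be reported, and 8.2.7 requires it in a by-arm table of subject incidence.
- 8.2.1 counts that subject once in each group. The natural result is 1/52 = 1.9% under ciNPT and 1/52 = 1.9% under control: one event shown twice.
- If it is judged related, 7.2.1 does not say to which product, so the row for related events has no defined arm either.

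Now suppose skin stripping under one dressing, a local risk listed in section 6. It is not a named SSC category in 4.15.1 and enters there only if it needs intervention. Otherwise it reaches the report through the AE record, where 7.4 lists no side.

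**2. Effect on a pooled row.** Let s be the proportion of subjects with a systemic TEAE, and t and c the proportions of ciNPT and control knees with a local TEAE. Assume that local events are correctly attributed to a knee, that systemic events are counted in both arms, and that the two kinds occur independently.

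- Arm incidence: 1 − (1 − s)(1 − t) for ciNPT and 1 − (1 − s)(1 − c) for control.
- Risk difference: (1 − s)(t − c). Only subjects without a systemic event can contribute to it.

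The rates below are assumptions.

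| Local rates (ciNPT, control) | s | ciNPT arm | Control arm | Risk difference | Risk ratio |
|---|---|---|---|---|---|
| 15%, 5% | 0 | 15% | 5% | 10 points | 3.00 |
| 15%, 5% | 20% | 1 − 0.80×0.85 = 32% | 1 − 0.80×0.95 = 24% | 8 points | 1.33 |
| 15%, 5% | 40% | 1 − 0.60×0.85 = 49% | 1 − 0.60×0.95 = 43% | 6 points | 1.14 |
| 15%, 5% | 60% | 1 − 0.40×0.85 = 66% | 1 − 0.40×0.95 = 62% | 4 points | 1.06 |
| 20%, 10% | 0 | 20% | 10% | 10 points | 2.00 |
| 20%, 10% | 20% | 36% | 28% | 8 points | 1.29 |
| 20%, 10% | 40% | 52% | 46% | 6 points | 1.13 |
| 20%, 10% | 60% | 68% | 64% | 4 points | 1.06 |

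The limiting case is that local events also carry no knee and are counted in both arms. With 15% and 5%, and independent knees, each arm then shows 1 − 0.85×0.95 = 19.25% for local events. The difference is exactly zero whatever the true rates.

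**The case against.** The case against has real weight.

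- **A reader might infer that no knee is recorded for any AE.** The documents do not support that. The list in 7.4 is not said to be complete, the eCRF is not shown, the Safety Analysis Set presupposes attribution by knee, and SSCs and knee-related admissions and ED visits do record the knee. What stands is that the AE description does not list it. The Safety Set definition does not close that gap, because it relies on an attribution that 7.4 does not ask for.
- **A reader might infer that the plan puts systemic events in both arms.** It does not say so. Section 8.2.1 counts subjects, not events, and also allows an overall summary. Counting in both arms is the natural reading, but the defect is that no rule is given.
- **A reader might infer that every device difference is diluted.** That is too broad. Section 8.2.7 reports by system organ class and preferred term, and a pulmonary embolism row cannot dilute a row for a purely local term if the knee is recorded. Dilution affects pooled rows and classes that mix local and systemic terms. Rows for related events would leave out systemic events judged unrelated, though the product meant remains unspecified.
- **The consequence is descriptive.** No safety hypothesis test is planned. SSCs are a separate secondary endpoint assessed per knee, with McNemar's test among the options in 8.2.5, so a difference in SSCs would show there.
- **Detail is deferred to the later SAP (8.6).** That can settle table layout. It cannot recover a side that was never collected.

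**Conclusion.** The point holds in a limited form. A by-arm table of all TEAEs by subject incidence has no defined meaning for systemic events when every subject is in both arms. The documents supply neither a rule for those events, nor a listed knee field on the AE record, nor a relatedness judgement tied to one product.

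If systemic events are counted in both arms, the risk difference in pooled rows is multiplied by (1 − s): a 10-point local difference becomes 8, 6 or 4 points at systemic rates of 20%, 40% or 60%. This rests on assumed AE rates, on independence of local and systemic events, and on correct knee attribution of local events. The actual size cannot be fixed from the documents. Rows for study discontinuation are uninformative by arm in any case, because section 4.4.2 withdraws both knees together.

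The sponsor should correct this. It weakens the descriptive safety comparison and leaves the primary analysis untouched.

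**What to change.** - **Section 7.4 and the eCRF:** add a required AE field with the options right knee/leg, left knee/leg, both, and not knee-related. If the eCRF already has one, state it in 7.4.
- **Section 7.2.1:** record relatedness separately for each study dressing.
- **Section 8.2.7:** tabulate knee-attributed TEAEs by treatment received, per knee and as paired data. Report all other TEAEs once per subject in a single overall column.

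The cost is one eCRF field, a second relatedness entry and revised safety table shells. The field has to be in place while data are collected; the table layout can follow in the SAP.

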8.3. Additional Statistical Details

8.3.1. Sample Size Determination

Pichonnaz et al measured the limb volume utilizing the truncated cone method. The mean volume percentage difference from baseline to Day 8 post-surgery was 11.9%, with a standard deviation of 8.2% at Day 8.¹ In 2016, Pichonnaz et al used the same method to evaluate the lower limb volume and the mean percentage difference from baseline to postoperative Day 7 was 15.3%, with a standard deviation of 6.5% at Day 7.² Assuming in our study the control group has a percent change of 13.6% in volume from baseline to post-surgery Day 6-8, while the PREVENA RESTOR group holds a percent change of 8% in the same period, given the standard deviation is 9.2% in both groups, a total of **52**

subjects (assuming 15% dropout rate) are needed to achieve 80% power based on a two-sample t-test with a type I error rate of 0.05.

8.3.2. Randomization

All subjects who meet all inclusion criteria and no exclusion criteria will be randomized in a 1:1 ratio to receive the PREVENA RESTOR ARTHRO•FORM™ Incision Management System or the control in either right or left knee. Each subject will receive both treatments (one treatment per knee). A randomization schedule, including randomization numbers and treatment assignments, will be generated and maintained centrally in the web-based clinical database management system. Once randomized, a subject's assignment cannot be altered or changed; a subject should not be randomized twice. The randomization schedule will be kept blind to any person who is involved in the daily operations of the study. It will only be accessible to the study biostatisticians who generate and review the schedule, and the vendor's team members (if an EDC vendor is utilized) who are involved in reviewing the schedule and uploading the schedule.

8.4. Open-Label Study Reporting Results

All precautions will be taken to avoid introducing any form of bias during the conduct of the study. While the study is ongoing, summary statistics by treatment arms across all sites may be limited to a small group not involved in the daily operations of the study. Treatment arms may be masked in the summary reports or outputs (tables, listings, and figures) if needed. Summary statistics during the conduct of the study will not be shared with investigators and clinical sites. Upon study completion, the full results will be shared with all investigators and clinical sites.

8.5. Interim Analysis

No interim analysis is planned for this study.

8.6. Statistical Analysis Plan and Changes in Analyses

A Statistical Analysis Plan (SAP) containing full details of the statistical analyses and execution will be prepared for this study. The SAP (SAP) will be finalized prior to locking

the study database and the final analysis. Any changes from the planned analyses in this protocol or SAP will be noted in the Clinical Study Report (CSR).

9. HANDLING OF STUDY PRODUCTS

Study product receipt, use, dispensation, destruction, and return records will be maintained throughout the study.

Upon receipt of product, the investigator or designee will inventory the shipment and immediately notify the sponsor if the study product or other study supplies are missing. The monitor will verify that study product documentation is maintained appropriately during monitoring visits.

At the completion of the study, there will be a final reconciliation of study product shipped, used, and unused. Any unused study product and associated supplies will be returned to the sponsor.

10. DATA HANDLING AND RECORD KEEPING

10.1. Investigator/Study Site Training

The investigator and site staff will be trained on the protocol, the study products, and any specialized procedures prior to enrolling subjects into the study. The sponsor will provide support to site staff for any questions or concerns related to study products and procedures. The sponsor will not have any influence on subject medical care.

10.2. Electronic Case Report Form (eCRF) and Source Documents

Source documents include all information in original records, certified copies of original records, observations, or other activities necessary for the reconstruction and evaluation of the study. All source documents should be completed in their entirety in a neat, legible manner to ensure accurate interpretation of the data.

Data from source documents of each subject will be entered into the subject's electronic case report form (eCRF). Guidance for eCRF completion will be provided and reviewed with the site staff prior to receiving study product.

10.3. Monitoring of Study Data

The data will be entered into the clinical study database by Investigative site staff and verified for accuracy by a sponsor representative. The investigator will allow access to their clinical study records for periodic on-site monitoring visits by a designated sponsor representative, with the understanding that the representative is bound by professional secrecy and will not disclose a subject's identity or personal medical information. The representative will review eCRFs for completeness during on-site monitoring visits, and after the eCRFs are submitted; any discrepancies will be resolved with the investigator or designee, as appropriate.

10.4. Data Handling

The sponsor is responsible for compilation and verification of the clinical study data, retention of the clinical study database, performance of statistical analysis, and preparation of the CSR.

10.5. Records Retention

The study site will maintain all study documentation and institute measures to prevent the accidental or premature destruction of any data and/or documents related to the study.

After formal discontinuation or completion of the study, the investigator will retain all clinical study documentation for a minimum of two (2) years from the date the investigation is terminated or completed or in accordance with the regulations in effect for the jurisdiction where the site is located. The investigator will contact the sponsor prior to the destruction of any study records.

11. ADMINISTRATIVE REQUIREMENTS

11.1. Good Clinical Practice (GCP)

This study is to be conducted according to applicable national regulations where the study is being conducted, international standards of good clinical practice (GCP) such as the International Council for Harmonisation guidelines, and institutional research policies and procedures.

11.2. Ethical Considerations

This study will be conducted in accordance with ethical principles founded in the Declaration of Helsinki. Approving IRB/ECs will be provided all relevant study documentation to safeguard the rights, safety, and well-being of subjects as mandated. Participating investigators will obtain IRB/EC approval of the study prior to initiation at their sites. The protocol, IFUs, informed consent, written information given to subjects, safety updates, and any revisions to these documents will be provided to the IRB/EC by the investigator.

11.3. Subject Informed Consent

Written informed consent will be obtained from a potential subject after the study has been fully explained and prior to the conduct of any study-related procedures. Obtaining informed consent is a process that must be documented in compliance with GCP, IRB/EC, and other applicable regulatory requirements. The investigator is responsible for continuing an open conversation with the subject about their continued participation in the study. The sponsor will conduct periodic monitoring to ensure informed consent is obtained for each subject prior to any study procedures.

11.4. Confidentiality

Information collected about subjects during the study will be kept confidential and managed according to the requirements of the IRB/EC, Health Insurance Portability and Accountability Act of 1996 (HIPAA), and any additional requirements as required by the country/regulatory agency where the study is taking place.

In the event that a subject revokes an authorization to collect or use Personal Health Information (PHI), the investigator retains the ability to use all information collected prior to the revocation of subject authorization.

11.5. Clinical Trial Registration

A description of this study will be available on <http://www.ClinicalTrials.gov> and any other designated public study registry as required by applicable local and federal regulations. The description of the study that is made available will not include information that identifies subjects. At most, the website will include a summary of the results of the study and will be available for public review at any time. If required, the study may also be listed on additional clinical trial websites as required by the country/regulatory agency.

11.6. Auditing and Inspecting

Participation as an investigator in this study implies acceptance of potential inspection by government regulatory authorities and applicable compliance and quality assurance offices.

The investigator will permit study-related monitoring, audits, and inspections of all study-related documents (eg, source documents, regulatory documents, data collection instruments, study data) by the IRB/EC, sponsor or its designee, and government regulatory bodies.

12. PUBLICATION PLAN

The publication policy for this study will be addressed in a separate agreement.

